### **Recording Serious Adverse Events**

For SAEs, record the event(s) on both the CRF and the SAE Form.

The following should be considered when recording SAEs:

- Death is an outcome of an event. The event that resulted in the death should be recorded and reported on both an SAE Form and CRF.
- For hospitalizations, surgical, or diagnostic procedures, the illness leading to the surgical or diagnostic procedure should be recorded as the SAE, not the procedure itself. The procedure should be captured in the narrative as part of the action taken in response to the illness.

### **Pregnancy**

Notification to Drug Safety: Complete a Pregnancy Report Form for all pregnancies that occur from the time of first study drug dose until 6 months after the last dose of study drug(s), including any pregnancies that occur in the partner of a male study subject. Only report pregnancies that occur in a male subject's partner if the estimated date of conception is after the male subject's first study drug dose. Fax to the Sponsor's Drug Safety Department within 48 hours of becoming aware of a pregnancy. All pregnancies will be monitored for the full duration; all perinatal and neonatal outcomes should be reported. Infants should be followed for a minimum of 8 weeks.

Collection of data on the CRF: All pregnancies (as described above) that occur within 28 days of the last dose of study drug(s), will also be recorded on the Adverse Events and Pre-existing Conditions CRF.

Abortion, whether accidental, therapeutic, or spontaneous, should be reported as an SAE. Congenital anomalies or birth defects, as defined by the 'serious' criterion above (see definitions in Section 6.3.1.1) should be reported as SAEs.

#### **6.3.1.3 Reporting Periods for Adverse Events and Serious Adverse Events**

The safety reporting period for all AEs and SAEs is from date of consent through the follow-up visit. All SAEs that occur after the safety reporting period and are considered study treatment-related in the opinion of the Investigator should also be reported to the Sponsor. In addition, new-onset neuropathy, suspected PML, or other AEs/SAEs of interest will be reported until the end of the follow-up period.

Serious AEs will be followed until significant changes return to baseline, the event stabilizes (recovering/resolving) or is no longer considered clinically significant by the Investigator, or the subject dies or withdraws consent. All nonserious AEs will be followed through the safety reporting period. Certain nonserious AEs of special interest may be followed until resolution, return to baseline, the event stabilizes or is no longer considered clinically significant by the Investigator, the subject dies or withdraws consent, or study closure.

#### **6.3.1.4    *Serious Adverse Events Require Immediate Reporting***

Within 24 hours of observing or learning of an SAE or suspected case of PML, Investigators are to report the event to the Sponsor at the fax number below, regardless of the relationship of the event to the study treatment regimen.

SAE [contact]

For initial SAE reports, available case details are to be recorded on an SAE Form. At a minimum, the following should be included:

- subject number;
- date of event onset;
- description of the event; and
- study treatment, if known.

The completed SAE Form and SAE Fax Cover Sheet are to be faxed to the Sponsor's Drug Safety Department within 24 hours (see fax number above and as specified on the SAE report form).

Relevant follow-up information is to be submitted to the Sponsor as soon as it becomes available.

### **6.3.1.6 Sponsor Safety Reporting to Regulatory Authorities**

Investigators are required to report all SAEs, including anticipated SAEs, to the Sponsor (see Section [6.3.1.4](#)).

The Sponsor will report all SAEs to regulatory authorities as required per local regulatory reporting requirements.

### **6.3.2 Management of Infusion Reactions**

Infusion-related reactions may occur during the infusion of study treatment. The infusion should be administered at a site properly equipped and staffed to manage anaphylaxis should it occur. All supportive measures consistent with optimal subject care should be given throughout the study according to institutional standards. Supportive measures may include administering medications for infusion-related reactions.

Subjects who have experienced a Grade 1 or Grade 2 infusion-related reaction should be premedicated for subsequent infusions. Premedication may include acetaminophen and an antihistamine administered 30 to 60 minutes prior to each brentuximab vedotin infusion or according to institutional standards.

If anaphylaxis occurs, brentuximab vedotin administration should be immediately and permanently discontinued.

### **6.3.3 Progressive Multifocal Leukoencephalopathy Assessment**

Study site personnel and subjects will be educated regarding the signs and symptoms of PML. Close monitoring during the course of the study for any new symptoms or signs suggestive of PML will be performed, with regular neurologic examinations (including evaluation of cranial nerves, motor and sensory function, coordination, and mental status). The PML assessment will be conducted by a qualified individual and will be performed at screening and as indicated on the schedule of events (see [Table 3](#)).

If a subject has a positive finding on the PML assessment or if there is strong clinical suspicion for PML, the event should be expeditiously reported as an AE of special interest within 24 hours (see Section [6.3.1.4](#)). If PML is suspected, dosing with study drug for that subject will be suspended and the subject should be promptly referred to a neurologist. Following formal evaluation by a neurologist, further work up will include brain magnetic resonance imaging performed with and without contrast. If PML cannot be ruled out, a

lumbar puncture with cerebrospinal fluid analysis for JCV by polymerase chain reaction may be performed. If JCV is detected, the subject should be treated as a PML case, permanently discontinue study drug, and transfer to safety follow-up. Dosing with study drug can only be resumed in subjects where PML has been ruled out.

### 6.3.4 Anaphylaxis

Anaphylaxis will be defined by the criteria discussed in the statement paper from the Second Symposium on the Definition and Management of Anaphylaxis and reproduced in [Table 1](#).

**Table 1 Clinical Criteria for Diagnosing Anaphylaxis**

**Anaphylaxis is highly likely when any one of the following 3 criteria are fulfilled:**

1. Acute onset of an illness (minutes to several hours) with involvement of the skin, mucosal tissue, or both (eg, generalized hives, pruritus or flushing, swollen lips-tongue-uvula)  
*AND AT LEAST ONE OF THE FOLLOWING*
  - a. Respiratory compromise (eg, dyspnea, wheeze-bronchospasm, stridor, reduced PEF, hypoxemia)
  - b. Reduced BP or associated symptoms of end-organ dysfunction (eg, hypotonia [collapse], syncope, incontinence)
2. Two or more of the following that occur rapidly after exposure to a *likely allergen for that patient* (minutes to several hours):
  - a. Involvement of the skin-mucosal tissue (eg, generalized hives, itch-flush, swollen lips-tongue-uvula)
  - b. Respiratory compromise (eg, dyspnea, wheeze-bronchospasm, stridor, reduced PEF, hypoxemia)
  - c. Reduced BP or associated symptoms (eg, hypotonia [collapse], syncope, incontinence)
  - d. Persistent gastrointestinal symptoms (eg, crampy abdominal pain, vomiting)
3. Reduced BP after exposure to *known allergen for that patient* (minutes to several hours):
  - a. Infants and children: low systolic BP (age specific) or greater than 30% decrease in systolic BP\*
  - b. Adults: systolic BP of less than 90 mm Hg or greater than 30% decrease from that person's baseline

BP = blood pressure; PEF = peak expiratory flow.

\* Low systolic blood pressure for children is defined as less than 70 mm Hg from 1 month to 1 year, less than (70 mm Hg + [2 × age]) from 1 to 10 years, and less than 90 mm Hg from 11 to 17 years.

### 6.3.5 Clinical Laboratory Evaluations

Samples will be drawn for both central and local laboratories. Local laboratory testing will include institutional standard tests for evaluating safety and making clinical decisions.

The following laboratory assessments will be performed by the central laboratory (unless otherwise specified) to evaluate safety at scheduled time points (see [Table 3](#)) during the course of the study:

- CBC with differential: hemoglobin, hematocrit, RBC count, mean corpuscular hemoglobin, mean corpuscular hemoglobin concentration, mean corpuscular volume, red cell distribution width, WBC count with 5-part differential (neutrophils, lymphocytes, monocytes, eosinophils, and basophils), and platelet count;

Note: The results of the CBC must be available prior to administration of each dose; therefore, testing at these time points may be done by a local laboratory to facilitate availability of the results. In addition, separate CBC samples at all specified time points should be collected for central laboratory testing.

- B cell count as quantified by CD19+ cells on flow cytometry, if applicable (for subjects with prior B cell depletion therapy, see [Table 3](#));
- HbA1c;
- chemistry panel: sodium, potassium, chloride, bicarbonate, blood urea nitrogen, creatinine, uric acid, albumin, eGFR, glucose, total bilirubin, direct bilirubin, AST, ALT, alkaline phosphatase, lactate dehydrogenase, amylase, lipase, and creatine phosphokinase;
- eight-hour fasting lipid panel: total cholesterol, triglycerides, high-density lipoprotein, and low-density lipoprotein;
- urinalysis: dipstick urinalysis, spot urinary protein and creatinine, and microscopic examination of the urinary sediment; and
- pregnancy test for WOCBP (Note: testing will be performed locally only and results will be available prior to dosing).

In addition, viral serology (HIV, hepatitis B surface antigen, anti-hepatitis B surface antibody, anti-hepatitis B core antibody, hepatitis C, and JCV) and tuberculosis (QuantiFERON-TB Gold or tuberculin purified protein derivative) tests will be performed at screening only.

Clinical laboratory tests will be reviewed for results of potential clinical significance at all time points throughout the study. The Investigator will evaluate any change in laboratory values. If the Investigator determines a laboratory abnormality to be clinically significant, it is considered a laboratory AE; however, if the laboratory value abnormality is consistent with a current diagnosis, it may be documented accordingly.

### **6.3.6 Vital Signs, Physical Findings, and Other Safety Assessments**

Measurement of vital signs, physical examinations, and 12-lead ECG recordings will be performed at the time points indicated in the schedule of events (see [Table 3](#)) and recorded in the subject's medical records and CRF. New or worsened abnormalities from baseline should be reported as AEs, as appropriate.

Vital signs will include systolic and diastolic blood pressure, pulse rate, respiratory rate, and temperature after the subject has been seated for 5 minutes. Weight in kilograms will be measured in indoor clothing without shoes; height in centimeters is measured at screening only.

Complete physical examinations should include, but are not limited to, an assessment of head, eye, ear, nose, and throat, and cardiovascular, respiratory, gastrointestinal, musculoskeletal, dermatological, and neurological systems. See Section [6.3.3](#) for additional information on PML monitoring and neurological examinations.

Standard 12-lead ECGs will be recorded after the subject has rested in a supine position for at least 10 minutes and should be obtained from the same machine whenever possible. The Investigator or designee should review, sign, and date the ECG tracings. Paper copies will be filed in the subject's records at the site.

## **6.4 Pharmacokinetic Measurements**

### **6.4.1 Plasma Concentrations**

Sensitive, qualified assays will be used to measure drug analytes, including brentuximab vedotin (ADC), total antibody (TAb), and MMAE concentrations in serum or plasma. These assays will include enzyme-linked immunosorbent assays and liquid chromatography/tandem mass spectrometry assays, as well as other assays if further characterization is required.

Samples for PK analysis will be collected within 30 minutes prior to study drug administration and at the end of infusion (within 5 minutes) on study drug administration days (Days 1, 22, 43, and 64). Samples will also be collected between the first and second doses on Days 2, 3, 8, and 15 at approximately the same time of day as the end-of-infusion sample on Day 1, if possible. Additional samples will be collected any time on the day of collection during the observation period (Days 85 and 106) and at the follow-up visit on Day 127.

Up to approximately 700 mL of whole blood will be obtained from each subject for PK, PD, and safety assessments during the study.

The following information will be captured for blood sample collection in each subject's CRF:

1. subject's number and initial;
2. time and date of dose administration; and
3. time and date of each blood sample collected for PK analysis.

Please refer to the Laboratory Manual for sample collection and storage procedures.

#### **6.4.2 Antitherapeutic Antibodies**

Serum samples will be collected for the detection and characterization of antibodies against brentuximab vedotin in all subjects at the time points indicated in the schedule of events (see [Table 3](#)). Samples will be analyzed using validated assays.

### **6.5 Pharmacodynamic Measures**

Pharmacodynamic assessments will be performed as specified in the schedule of events ([Table 3](#)) and include the following:

- flow cytometry for specific lymphocyte populations that may include, but are not limited to, the following:
  - naïve T, TEM, TCM: CD4, CD30, CD45RA, CD153, CD3, CD197, and CD8;
  - Treg/Th1/Th2/Th17: CD4, CD30, CD127, CD183, CD153, CD25, CD3, CD196, CD8, and CD194;
  - naïve B, plasmablasts, plasma cells, memory B: CD19, CD30, CD38, IgD, CD153, CD10, CD27, CD138, and CD20;
  - macrophages, NK cells DCs: CD30/CD19, CD30, HLA-DR, CD16, CD153, CD11c, CD7, CD123, CD56, and CD14; and
- inflammatory markers, including: ESR, hsCRP, sCD30, and soluble CD153 (sCD153);
- autoantibody assays including, but not limited to:
  - ANA, as assessed by indirect immunofluorescence titer;
  - anti-dsDNA;
  - anti-C1q;

- anti-Smith antibodies (anti-Sm), anti-ribonucleoprotein (anti-RNP), anti-Sjögren's Syndrome A antibodies (anti-SSA), and anti-Sjögren's Syndrome B antibodies (anti-SSB);
- anticardiolipin, anti-β-2-glycoprotein I, lupus anticoagulant;
- direct Coombs test; and
- quantitative IgG, IgM, IgA, and IgE;
- complement studies: C1q, C3, C4, and CH50;
- lymph node or tonsil biopsies (optional):
  - T cell subpopulations such as, but not limited to:
    - CD4+ and CD4+CD30+, and subpopulations of each, such as: CD25+ or Foxp3+, interferon (IFN) $\gamma$ + or CXCR3+, IL-4+ or CCR4+, and IL-17+ or CCR7+;
    - CD8+ and CD8+CD30+;
  - B cell subpopulations such as, but not limited to, naïve and memory, plasmablasts and plasma cells; and
  - germinal center structure.

In addition, a serum sample will be collected for possible future testing of SLE-related cytokines, such as, but not necessarily limited to, IFN- $\alpha$ , BAFF, and cytokine TNF-like weak inducer of apoptosis (TWEAK).

Also, RNA sampling as specified in the schedule of events ([Table 3](#)) will consist of retention of a peripheral blood RNA sample for possible future testing of genome-wide SLE-related inflammatory gene expression patterns, such as via microarray or RNA-seq.

## 6.6 Pharmacogenetic Sampling

For subjects who provide additional consent, a de-identified blood sample will be collected at baseline for potential future research.

## 6.7 Appropriateness of Measurements

All efficacy, safety, PK, and PD assessments used in this study are widely used and generally recognized as reliable, accurate, and relevant.

## 7.0 QUALITY CONTROL AND QUALITY ASSURANCE

According to the Guidelines of Good Clinical Practice (GCP) (CPMP/ICH/135/95), the Sponsor is responsible for implementing and maintaining quality assurance and quality control systems with written Standard Operating Procedures (SOPs).

Quality control will be applied to each stage of data handling.

The following steps will be taken to ensure the accuracy, consistency, completeness, and reliability of the data:

- Investigator meeting(s);
- central laboratories for clinical laboratory parameters and ECGs;
- site initiation visit;
- early site visits post enrollment;
- routine site monitoring;
- ongoing site communication and training;
- data management quality control checks;
- continuous data acquisition and cleaning;
- internal review of data; and
- quality control check of the final clinical study report.

In addition, the Sponsor and/or Quintiles Clinical Quality Assurance Department may conduct periodic audits of the study processes including, but not limited to, study site, site visits, central laboratories, vendors, clinical database, and final clinical study report. When audits are conducted, access must be authorized for all study-related documents including medical history and concomitant medication documentation to authorized Sponsor's representatives and regulatory authorities.

### 7.1 Monitoring

The Sponsor has engaged the services of a contract research organization, Quintiles, to perform all monitoring functions within this clinical study. Quintiles' monitors will work in accordance with Sponsor or Quintiles' SOPs and have the same rights and responsibilities as

monitors from the Sponsor organization. Monitors will establish and maintain regular contact between the Investigator and the Sponsor.

Monitors will evaluate the competence of each study site, informing the Sponsor about any problems relating to facilities, technical equipment, or medical staff. During the study, monitors will check that written informed consent has been obtained from all subjects correctly and that data are recorded correctly and completely. Monitors are also entitled to compare entries in CRFs with corresponding source data and to inform the Investigator of any errors or omissions. Monitors will also control adherence to the protocol at the study site. They will arrange for the supply of study drug and ensure appropriate storage conditions are maintained.

Monitoring visits will be conducted according to the United States CFR Title 21 parts 50, 56, and 312 and ICH Guideline for GCP. Monitoring visits will be made to each site while subjects are enrolled in the study. The monitor will make written reports to the Sponsor on each occasion contact with the Investigator is made, regardless of whether it is by phone or in person.

During monitoring visits, entries in the CRFs will be compared with the original source documents (source data verification). For all items, this check will be 100%.

## **7.2 Data Management/Coding**

Data generated within this clinical study will be handled according to the relevant SOPs of the data management and biostatistics departments of Quintiles. The data will be inspected for inconsistencies by performing validation checks.

Adverse events will be coded using the Medical Dictionary for Regulatory Activities (MedDRA). Concomitant medications will be coded using the World Health Organization (WHO) drug dictionary. Concomitant diseases will be coded using MedDRA.

## **7.3 Quality Assurance Audit**

Study sites, the study database, and study documentation may be subject to a Quality Assurance audit during the course of the study by the Sponsor or Quintiles on behalf of the Sponsor. In addition, inspections may be conducted by regulatory bodies at their discretion.

## 8.0 STATISTICS

### 8.1 Determination of Sample Size

Since no prior studies in SLE have been conducted with brentuximab vedotin, the primary objective of this study is to evaluate the safety and tolerability of brentuximab vedotin in this patient population. As such, the number of subjects planned has been based on clinical judgment, to provide sufficient experience upon which to design a larger efficacy (Phase 2) study. Study measurements of efficacy, safety, PK, and PD will be listed and summarized by dose and treatment group. Comparisons between brentuximab vedotin-treated subjects and placebo-treated controls will be performed, where applicable.

### 8.2 Statistical Methods

Data will be analyzed by Quintiles Inc. biostatistical staff. All details regarding the statistical analysis and the preparation of tables, listings, and figures will be described in the Statistical Analysis Plan prepared by Quintiles and approved by the Sponsor before database lock.

Summaries for safety and efficacy data collected will be presented for each treatment group, ie, for brentuximab vedotin 0.3, 0.6, 1.2, or 1.8 mg/kg IV every 3 weeks and placebo at each scheduled visit/assessment. Placebo subjects across cohorts will be aggregated for analysis. Subjects will be evaluated according to the treatment received.

For qualitative parameters, the population size (N for sample size and n for available data) and the percentage (of available data) for each class of parameters will be presented. Quantitative parameters will be summarized by the population size (N for sample size and n for available data), the mean, the standard deviation, the median, 25th percentile, 75th percentile, the minimum, and the maximum values. Geometric means and coefficients of variation will be included as deemed relevant.

A nominal significance level of 5% will be used for exploratory inference testing.

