## 4.0 INVESTIGATIONAL PLAN

### 4.1 Summary of Study Design

This is a multicenter, randomized, placebo-controlled, double-blind, multiple-ascending-dose study to evaluate the safety and tolerability of brentuximab vedotin in subjects with active SLE. Approximately 40 subjects in 4 dosing cohorts (10 subjects per cohort) are planned for study participation at approximately 20 study sites in the US. Subjects who meet inclusion and exclusion criteria will be randomly assigned in a 4:1 ratio within each dosing cohort to receive IV brentuximab vedotin or placebo every 3 weeks (Days 1, 22, 43, and 64) for a total of 4 doses. The following doses are planned for each ascending dose cohort:

[figure not shown]
- 0.3 mg/kg IV every 3 weeks for 4 doses;
- 0.6 mg/kg IV every 3 weeks for 4 doses;
- 1.2 mg/kg IV every 3 weeks for 4 doses; and
- 1.8 mg/kg IV every 3 weeks for 4 doses.

There will be a total of 10 subjects in each dose cohort with 8 subjects randomly assigned to each of the 4 brentuximab vedotin doses and 2 subjects to placebo (for a total of 8 placebo subjects overall). Initiation of enrollment at the next dose level will only commence after the final subject of each cohort has been evaluated at the Day 43 visit, and upon endorsement of the SMC following review of the safety data. Depending on the findings, the SMC may recommend additional enrollment of subjects at specific dose levels to better characterize the safety of a particular dose, or may recommend different dose regimens based on the emerging safety data. When available from each full cohort, the SMC will review all Day 85 safety data and may recommend that an already enrolled succeeding dose cohort be discontinued, or its treatment regimen truncated. Doses are not to exceed 1.8 mg/kg IV every 3 weeks or equivalent. Up to 20 subjects total may be enrolled via additional SMC-recommended cohorts for a total of up to 60 subjects.

Assessments for safety (including PML monitoring, see Section 6.3.3), efficacy, PK, and PD will be performed at the times indicated in the schedule of events (see [Table 3](#)). Following the last dose of study drug, there will be a 6-week observation period (through Day 106) and a follow-up visit will take place at Day 127.

A flowchart of the study design is presented in [Figure 1](#).

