### **5.3 Method of Assigning Subjects to Treatment Group**

Once the subject meets inclusion and exclusion criteria and has provided written informed consent, the study site will request the study medication assignment using the Interactive Web Response System (IWRS).

A total of 10 subjects in each dose cohort will be randomly assigned in a 4:1 ratio, resulting in 8 subjects assigned to each of the 4 brentuximab vedotin dose cohorts and a total of 8 subjects assigned to placebo (2 per cohort).

To randomly assign a subject to treatment, the study site will use the internet to access the IWRS. Subjects will be assigned their 6-digit subject number, starting with a 3-digit site number followed by a hyphen and a 3-digit sequential number (eg, 101-001). The IWRS will provide the study drug kit number(s) of the blinded study drug to be dispensed.

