15.2.1.2. ANALYSIS

The following analyses will be performed for all study days with Day 85 specified as the secondary endpoint, and all other visits falling under exploratory analyses.

The percentage of subjects demonstrating SRI Response will be presented by treatment with 95% CI using Wilson's score method (SAS PROC FREQ syntax: table response/binomial (wilson)). Comparisons between each active treatment group and placebo will be performed using Fisher's exact test (two-sided). The ratio of percentages (relative risk) for active to placebo will be presented for each dose level with corresponding 95% CI, based on the score method [Farrington] (SAS PROC FREQ syntax: table trta*response / relrisk(method=score equal)). Percentages with Wilson 95% CI will be plotted versus study day per treatment, with all treatments overlain.

Logistic regression of the log odds of SRI response on log2 dose level (mg/kg) will be performed. Placebo subjects will be treated as a having dose of 0 mg/kg. Based on this model, the estimate of the slope and odds ratio (OR) for a doubling of dose will be presented with 95% CI (based on the profile likelihood) and two-sided p-value (Wald test).

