15.3.3.2. ANALYSIS

Observed and change values will be summarized by treatment group. Means with 95% CI will be plotted for Observed and CFB values over time with treatment groups overlaid. Individual values over time will be plotted over time per treatment group.

An analysis of covariance model will be fit for CFB/CFEOT at each scheduled time, with a fixed effect for treatment group and a covariate for the baseline value. Comparisons will be made between each dose level, and all active treated subjects combined versus placebo at the 5% significance level (two-sided). Least-squares treatment means and mean differences will be estimated with 95% CI and two-sided p-values for the test of no treatment difference.

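### Randomisation is within sequential dose cohorts, but placebo is pooled and cohort is in no planned model, so drift between cohorts enters the per-dose contrasts (mainly the lowest and highest dose) and the dose slope

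*Protocol*

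**What the plan says.** Protocol 5.3: "A total of 10 subjects in each dose cohort will be randomly assigned in a 4:1 ratio", which gives 8 active and 2 placebo subjects per cohort. Under Protocol 4.1, enrolment at the next dose "will only commence after the final subject of each cohort has been evaluated at the Day 43 visit" and the safety committee has endorsed it.

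For analysis, Protocol 8.2 says "Placebo subjects across cohorts will be aggregated for analysis", and SAP 6.1 repeats this. SAP 7.1 names the baseline value as the only covariate. SAP 7.2 deals with site or region, not cohort.

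- **SRI response (SAP 15.2.1.2):** unstratified two-sided Fisher tests and relative risks for each dose against placebo. Also: "Logistic regression of the log odds of SRI response on log2 dose level (mg/kg) will be performed".
- **Continuous endpoints (SAP 15.3.3.2, copied by the other continuous efficacy and PD endpoints):** an ANCOVA "with a fixed effect for treatment group and a covariate for the baseline value". It compares each dose, and all active subjects combined, with placebo.

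Protocol 8.2 sets the standard: "A nominal significance level of 5% will be used for exploratory inference testing".

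**The concern.** Among active subjects, dose and cohort are the same variable. Randomisation makes subjects comparable within a cohort (8 versus 2). The planned per-dose tests compare 8 subjects from one cohort with 8 placebo subjects, of whom only 2 were enrolled alongside them. Such a test has no drug effect and no change between cohorts as its joint null hypothesis. Because dose rises with calendar order, a steady change in background looks like a dose-response.

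Some change is plausible. SLEDAI, BILAG and PhGA are investigator-scored. Each cohort opens after endorsement of a higher dose. The last subject of cohort 1 and the first of cohort 4 are at least 3 × 6 = 18 weeks apart, plus recruitment time.

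What is at stake is dose choice: Protocol 8.1 says the study should support the design of a larger efficacy study.

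**Working it through.** **Inputs from the documents.** Four cohorts of 10 at 4:1 give 8 active and 2 placebo per cohort, so N = 40 and 8 placebo in total, as Protocol 5.3 states. Tests are two-sided at 5%. No effect size, SD, response rate or power is given.

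**Assumptions.** No drug effect. Background moves linearly by a total of D residual SD from cohort 1 to cohort 4. The baseline covariate is unrelated to the drift.

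**Bias of a dose contrast.** It equals the cohort's background minus the four-cohort mean, because pooled placebo has 2 subjects from each cohort. Backgrounds are 0, D/3, 2D/3 and D, with mean D/2. The biases are −D/2, −D/6, +D/6 and +D/2 for 0.3, 0.6, 1.2 and 1.8 mg/kg.

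**Bias of all active versus placebo.** Both groups average D/2, so the bias is 0.

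**Rejection rates of the planned five-group model (simulation):**

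| Total drift D | Bias, 0.3 and 1.8 mg/kg | Rejects | Bias, 0.6 and 1.2 mg/kg | Rejects | Any dose | All active |
|---|---|---|---|---|---|---|
| 0 | 0 | 5% | 0 | 5% | 15% | 5% |
| 0.5 SD | ±0.25 SD | 7-8% | ±0.08 SD | 5-6% | 20% | 5% |
| 1 SD | ±0.50 SD | 15-16% | ±0.17 SD | 6% | 36% | 5% |
| 1.5 SD | ±0.75 SD | 27-29% | ±0.25 SD | 7% | 57% | 5% |

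**Fisher 8 versus 8 (exact enumeration).**
- Flat 35% background: 1.6% rejection per dose.
- Background 20/30/40/50%: bias from −15 to +15 percentage points; the highest rate is 4.1%, at the top dose.
- Extreme drift, 10/30/50/70%: bias from −30 to +30 points; 11.7% at the top dose.

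**SRI dose slope (Wald test).** The SAP sets placebo to 0 mg/kg, where log2 is undefined, so the rate depends on a coding that the SAP does not give. For background rising from 20% to 50%, the slope rejects 22% with active doses only (median odds ratio 1.72 per doubling) and 14-15% with placebo given a workable low-dose coding. Without drift it rejects 3.9-4.4%. For background rising from 20% to 60%, it rejects 37% with placebo dropped, but 19%, 8% and 5% with placebo coded as 0.15, 0.03 and 0.01 mg/kg. The direction is clear; no single rate can be attached to the model as written.

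**Loss of balance.** Suppose both cohort-4 placebo subjects have no Day 85 value. The active mean is D/2 and the placebo mean is (0 + D/3 + 2D/3)/3 = D/3. The planned all-active contrast is then biased by D/6, which is 0.17 SD at D = 1 and 0.25 SD at D = 1.5. Rejection is about 6-9%. A model with active/placebo, cohort and baseline stays at about 5%.

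**Cost of including cohort.**
- All active, residual df: planned model 40 − 5 groups − 1 baseline = 34; cohort model 40 − 4 cohorts − 1 active/placebo − 1 baseline = 34.
- All active, SE: unstratified √(1/32 + 1/8) = 0.395 SD; stratified √[(1/8 + 1/2)/4] = 0.395 SD.
- All active, power for a 1 SD effect: 68% with either model without drift; 66% (planned) and 67% (cohort) at 1 SD drift.
- Per dose, SE: pooled √(1/8 + 1/8) = 0.50 SD; own cohort only √(1/8 + 1/2) = 0.79 SD, which is 1.58 times larger.

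**The case against.** **Pooling is deliberate, and the study is exploratory.** Protocol 2.5 wants a placebo group comparable in size with each dose group, as in earlier SLE studies. There is no efficacy primary endpoint, and SAP 7.4 calls the study hypothesis-generating; with no drift the plan already accepts about 15% any-dose error. This stands, and it limits the weight of the point. It does not remove the bias in the estimates, which a nominal label leaves untouched.

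**Nothing shows that drift occurs.** True. Entry criteria are common to all cohorts, background drugs must be stable, and the baseline covariate can absorb drift that shows in baseline scores. It cannot absorb drift in later response or scoring.

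**Two placebo subjects per cohort are too few for adjustment.** Correct for single doses. Within-cohort Fisher on 8 versus 2 has a smallest possible p of 1/45 = 0.022. A cohort-stratified dose slope would use only active-versus-placebo gaps, so it is too weak, and not a clean enough test of dose-response, to overrule the planned slope.

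Two stronger readings are tempting, and the documents support neither:
- A reader might infer that drift distorts every planned test. The all-active contrast is balanced 8:2 in each cohort, the middle doses barely move, and Fisher's test is conservative.
- A reader might infer that no planned output could reveal drift. SAP 6.4 and Appendix 1 provide subject listings that carry dates, and SAP 15.3 provides individual plots, so cohorts could be reconstructed. What is missing is a planned display of placebo by cohort.

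**Conclusion.** The concern holds for the per-dose contrasts, chiefly at 0.3 and 1.8 mg/kg, and for any dose slope. Under assumed linear drift the extreme-dose estimates are off by half the total drift, and their ANCOVA tests reach about three times nominal at 1 SD. At 0.5 SD the inflation is small. The drift sizes are assumptions, and steady drift in one direction is the unfavourable pattern for the slope.

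The all-active comparison needs no bias repair under complete 8:2 cohorts. Including cohort there is worthwhile because it matches the randomisation at no cost in precision. It also protects the comparison if unimputed missing data (SAP 7.3), or the up to 20 extra subjects allowed by Protocol 4.1, upset the balance.

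The consequence falls on dose choice for the next study, not on a confirmatory claim. The undefined placebo coding in the logistic model is a separate matter.

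**What to change.** Before unblinding:

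1. In SAP 7.1 and 15.3.3.2, fit all active versus placebo with terms for active/placebo, cohort and baseline.
2. In SAP 15.2.1.2, add a cohort-stratified comparison of all active versus placebo for SRI response, such as an exact conditional test.
3. Show placebo results by cohort, 2 subjects each, beside the pooled displays.
4. Label the per-dose contrasts and the dose slope as descriptive and partly non-concurrent, since 2 of the 8 placebo subjects are concurrent with any one dose.
5. Give cohort-adjusted per-dose estimates as a sensitivity analysis only, with the wider SE stated (about 0.79 versus 0.50 SD).

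The cost is SAP wording, a few more model runs and one more display. Cohort is already known for every subject. Item 1 loses no residual degrees of freedom or power; the precision cost lies in item 5, which is why it does not replace the pooled contrasts.
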